7.1. Data presentation description

The following decimal description will be used for the demography and safety/reactogenicity.

Display Table	Parameters	Number of decimal digits
All summaries	% of count, including LL & UL of CI	1
All summaries	% of difference, including LL & UL of CI	2
Demographic characteristics	Mean, median age	1
Demographic characteristics	SD (age)	2
Immunogenicity	GMT ratio	2

The following data presentation description will be used for the immunogenicity analyses.

Statistical Analysis Plan

Study alias & e-track number(s): NTHI MCAT-001 (201281)

Component	GMC/T	Assay		Assay cut-off	Number of decimal digits		Tick marks on RCC's		
		method	Unit		GMC/T	GMC/T ratio			
						Low value	High value		
Anti-PD	GMC	ELISA	EL.U/mL	153	1	2	1	10000	
Anti-PE	GMC	ELISA	EL.U/mL	8	1	2	1	10000	
Anti-PiA	GMC	ELISA	EL.U/mL	7	1	2	1	10000	
Anti-UspA2	GMC	ELISA	EL.U/mL	18	1	2	1	10000	

8. CONDUCT OF ANALYSES

8.1. Sequence of analyses

- The analysis of data up to Visit 6 (Day 90, end of Epoch 001) will be performed in a first step. This analysis will include:
 - The final analysis of all immunogenicity results (including CMI), solicited AEs post-Dose 1 and post-Dose 2,
 - The assessment of unsolicited AEs up to 30 days post-Dose 1 and post-Dose 2, and of SAEs and pIMDs up to 30 days post-Dose 2 on as cleaned as possible data. No individual listings will be written at this stage.

This analysis will be documented in a statistical report. At this point, the GSK statistician will be unblinded (i.e. will have access to the individual subject treatment assignments).

- The analysis of Epoch 002 (from Visit 7 [Day 210] up to Visit 8 [Day 420]) will be performed in a second step, once those data will be available and cleaned. This analysis will include:
 - The final analysis of all immunogenicity results (including CMI) up to Visit 8 (Day 420).
 - SAEs and pIMDs up to Visit 8 (Day 420) on cleaned data.

In addition, all previous analyses will be re-produced based on cleaned data at this point.

Individual listings will only be provided at this stage.

Description	Analysis ID	Disclosure Purpose
Analysis up to Visit 6 (Day 90)	E1_02	Internal
Final analysis (up to day 450)	E1_01	CTRS & Clinical Study Report

Study alias & e-track number(s): NTHI MCAT-001 (201281)

8.2. Statistical considerations for interim analyses

Not applicable.

9. CHANGES FROM PLANNED ANALYSES

None.

The complete statistical analysis plan and results presentation is divided into 2 parts: the first part detailing the analyses to be performed (known as SAP, current document) and a second part, annex (-es) (called TFL) describing the flow and format of tables, figures and listings to be annexed to the SR.

LIST OF ABBREVIATIONS

AE	Adverse event
AECOPD	Acute exacerbation of COPD
ALT	Alanine aminotransferase
ATP	According-To-Protocol
ANCOVA	Analysis of covariance
CI	Confidence Interval
CMI	Cell-mediated immunity
COPD	Chronic obstructive pulmonary disease
CRF	Case Report Form
CTRS	Clinical Trial Registry
EL.U/ml	ELISA unit per milliliter
ELISA	Enzyme-linked immunosorbent assay
Eli Type	Internal GSK database code for type of elimination code
FEV ₁	Forced expiratory volume in 1 second
FVC	Forced vital capacity
FU	Internal GSK database code for Follow-up analysis (elimination codes) link to FORM-BIO-CLIN-9004-05 Criteria for eliminating subjects from the analyses
GMC	Geometric mean antibody concentration
GOLD	Global Initiative for Chronic Obstructive Lung Disease
GSK	GlaxoSmithKline
H. influenzae	Haemophilus influenzae
ICF	Informed consent form
ICS	Intracellular cytokine staining
IU/ml	International units per milliliter
LL	Lower Limit of the confidence interval

Statistical Analysis Plan

Study alias & e-track number(s): NTHI MCAT-001 (201281)

MA	Internal GSK database code for Main analysis (elimination codes) link to FORM-BIO-CLIN-9004-05 Criteria for eliminating subjects from the analyses
MATEX	MATerial EXcellence
M. catarrhalis	Moraxella catarrhalis
MedDRA	Medical Dictionary for Regulatory Activities
N.A.	Not Applicable
NTHI	Non-Typeable Haemophilus influenzae
PBMC	Peripheral blood mononuclear cell
PCR	Polymerase chain reaction
PD	Protein D
PE	Protein E
PI	Prescribing information
PilA	Type IV pili subunit of non-typeable Haemophilus influenzae
pIMD	Potential immune-mediated disease
PT	Preferred term
SAE	Serious adverse event
S. aureus	Staphylococcus aureus
SAP	Statistical Analysis Plan
SBIR	GSK Biological's Internet Randomization System
SD	Standard Deviation
SR	Study Report
STGG	Skim milk, tryptone, glucose, and glycerin transport medium
SYN	Synopsis
TFL	Tables Figures and Listing template annexed to SAP
TVC	Total vaccinated cohort
UL	Upper Limit of the confidence interval
UspA2	Ubiquitous surface protein A2 of Moraxella catarrhalis
VE	Vaccine efficacy

Statistical Analysis Plan

Study alias & e-track number(s): NTHI MCAT-001 (201281)

1. DOCUMENT HISTORY

Date	Description	Protocol Version
11-MAR-2016	Version 1	Amendment 1 – 30JUL2015
27-JUN-2016	Amendment 1 – Anti-PD cut-off was updated from 100 EL.U/mL to 153 EL.U/mL following the development of the new anti-PD test.	Amendment 1 – 30JUL2015
6-DEC-2016	Amendment 2 – Update the desirability function in order to take into account the Mcat Protein.	Amendment 1 – 30JUL2015

2. RATIONALE FOR THE AMENDMENT

Summary score's formulas have been updated, taking into account MCat protein according to the rules described in section 7 Statistical Methods.

3. STUDY DESIGN

The following group names will be used for the statistical analyses:

Group order in tables	Group label in tables	Group definition for footnote	Pooled Groups label in tables	Pooled definition for footnote
1	10-10-10	2 doses of non-adjuvanted NTHI/Mcat vaccine containing 10 mcg of PD, PE-PiA and UspA2		
2	10-10-10-AS	2 doses of AS01E-adjuvanted NTHI/Mcat vaccine containing 10 mcg of PD, PE-PiA and UspA2		
3	10-10-3-AS	2 doses of AS01E-adjuvanted NTHI/Mcat vaccine containing 10 mcg of PD, PE-PiA and 3 mcg of UspA2		
4	PLACE1	2 doses of saline solution – Step 1	Placebo	2 doses of saline solution
5	PLACE2	2 doses of saline solution – Step 2	Placebo	

4. OBJECTIVES

4.1. Primary objective

- To evaluate the safety and reactogenicity profile of the NTHI-Mcat investigational vaccines.

Study alias & e-track number(s): NTHI MCAT-001 (201281)

4.2. Secondary objective

- To evaluate the humoral and cellular immune response of the NTHI-Mcat investigational vaccines.

4.3. Tertiary objective

- To collect blood samples for assay development/validation and/or for evaluation/characterisation of the humoral and cellular immune responses to components of either the NTHI-Mcat investigational vaccines and/or of other respiratory pathogens.

5. ENDPOINTS

5.1. Primary endpoints

- Occurrence of each solicited local and general AE, during a 7-day follow-up period (i.e. day of vaccination and 6 subsequent days) post-Dose 1 and post-Dose 2, in all subjects, in all vaccine groups.
- Occurrence of any unsolicited AEs, during a 30-day follow-up period (i.e. day of vaccination and 29 subsequent days) post-Dose 1 and post-Dose 2, in all subjects, in all vaccine groups.
- Occurrence of haematological and biochemical laboratory abnormalities, after vaccination, in all subjects, in all vaccine groups:
 - Any haematological (RBC, WBC and differential count, platelets count and haemoglobin level) or biochemical (ALT, AST and creatinine) laboratory abnormality on Day 7, Day 60, Day 67, Day 210 and Day 420.
- Occurrence of any SAE, occurring from first vaccination (Day 0) to study conclusion (Day 420) in all subjects, in all vaccine groups.
- Occurrence of any pIMD occurring from first vaccination (Day 0) to study conclusion (Day 420) in all subjects, in all vaccine groups.

5.2. Secondary endpoints

- Humoral immune response to the components of the NTHI-Mcat vaccine formulations, on Day 0, Day 30, Day 60, Day 90, Day 210 and Day 420, in all subjects, in all vaccine groups:
 - Anti-PD, anti-PE, anti-PilA and anti-UspA2 antibody concentrations.

Study alias & e-track number(s): NTHI MCAT-001 (201281)

- Cell-mediated immune response to components of the NTHI-Mcat vaccine formulations, on Day 0, Day 60, Day 90, Day 210 and Day 420, in a sub-cohort of subjects, in all vaccine groups:
 - Frequency of specific CD4⁺/CD8⁺ T-cells measured on cryopreserved peripheral blood mononuclear cells (PBMCs) and identified by flow cytometry intracellular cytokine staining (ICS) expressing two or more markers (such as IL-2, IL-13, IL-17, IFN- γ , TNF- α and CD40L).

6. STUDY POPULATION

The following subject cohorts will be evaluated.

6.1.1. Total vaccinated cohort

The total vaccinated cohort (TVC) will include all subjects with at least one vaccine administration documented:

- A safety analysis based on the TVC will include all vaccinated subjects.
- An immunogenicity analysis based on the TVC will include all vaccinated subjects for whom immunogenicity data are available.

The TVC analysis will be performed per treatment actually administered at Dose 1.

6.1.2. According-to-protocol cohort

The ATP cohorts will be defined by epoch and will consist of all subjects from the TVC who will comply with eligibility criteria, study procedures up to the end of the epoch and had immunogenicity results in the epoch.

6.1.2.1. According-to-protocol cohort for analysis of immunogenicity (Epoch 001)

The ATP cohort for immunogenicity will include all subjects in the TVC:

- Who met all eligibility criteria.
- For whom the administration route and site of the vaccines was according to protocol.
- Who complied with the vaccination schedule.
- Who did not receive a concomitant medication/ product/vaccine leading to the elimination from the ATP analysis up the one month post-Dose 2 visit (Visit 6, Day 90).

Statistical Analysis Plan

Study alias & e-track number(s): NTHI MCAT-001 (201281)

- Who did not present with an intercurrent medical condition leading to elimination from the ATP analysis up to the one month post-Dose 2 visit (Visit 6, Day 90).
- Who complied with the immunogenicity blood sample timings at 1 month post-Dose 2 visit (Visit 6, Day 90).
- For whom post-Dose 2 immunogenicity results are available for at least one assay.

6.1.2.2. According-to-protocol cohort for analysis of persistence of immunogenicity (Epoch 002)

The ATP cohort for persistence of immunogenicity will include all evaluable subjects, i.e., those who were included in the ATP cohort for immunogenicity, or were excluded from this cohort solely because they had no blood samples taken or because of non-compliance with blood sample timings up to the one month post-Dose 2 visit (Visit 6, Day 90), and:

- Who did not receive a concomitant medication/ product/vaccine leading to elimination from the ATP analysis for immunogenicity.
- Who did not present with an intercurrent medical condition leading to elimination from the ATP analysis for immunogenicity.
- Who complied with at least one of the blood sample timings after the one month post-last vaccination visit (Visit 6, Day 90).
- For whom persistence immunogenicity results are available for at least one assay in at least one of the two persistence time points (Visit 7, Day 210 and Visit 8, Day 420).

The list of applicable elimination codes for each cohort can be found in the study specific form FORM-BIO-CLIN-9004-05 Criteria for eliminating subjects from the analyses.

Cohort	Elimination codes	Eli Type
ATP cohort for analysis of immunogenicity	1010-2500	MA
ATP cohort for analysis of persistence of immunogenicity	1010-2500	FU

7. STATISTICAL METHODS

7.1. Analysis up to Visit 6 (Day 90)

The final analyses will be descriptive and will be presented by study group, with pooled data from the two steps for the placebo groups.

Study alias & e-track number(s): NTHI MCAT-001 (201281)

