1.2.3. Rationale for the use of placebo

The placebo group (saline solution) is included in the NTHI MCAT-001 study as a control for both safety and immunogenicity assessments.

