5.2.2.2.1. Study group and treatment number allocation

The target will be to enrol approximately 120 eligible subjects who will be randomly assigned per step:

- **Step 1:** two study groups in a (1:1) ratio (approximately 15 subjects per group).
- **Step 2:** three study groups in a (1:1:1) ratio (approximately 30 subjects per group).

Allocation of the subject to a study group at the investigator site will be performed using SBIR.

Subjects will be minimised for centre at Step 1. At Step 2, subjects will be minimised for age (50-59 years or 60-70 years), for smoking status (current or former smokers), for centre and for forced expiratory volume in 1 second (FEV₁) / forced vital capacity (FVC) (≥ 0.7 or < 0.7). Minimisation factors will have equal weight in the minimisation algorithm.

As several minimisation factors have been defined for the treatment allocation at Step 2, it was decided at the design phase not to minimise for the CMI group allocation. This wouldn't be feasible from an implementation point of view. (Amended 16 March 2016)

After obtaining the signed and dated ICF from the subject (at Screening Visit) and after having checked the eligibility of the subject, the dedicated study staff will access SBIR (at Visit 1). Upon providing the information for each minimisation factor and the subject identification number, the randomisation system will determine the study group and will provide the treatment number to be used for the first dose. This treatment number will be used by the dedicated staff member for administration of the vaccine.

The number of each administered treatment must be recorded in the eCRF on the Vaccine Administration screen.

When SBIR is not available, please refer to the SBIR user guide or the Study Procedures Manual (SPM) for specific instructions.

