10.6. Statistical analysis

The final analyses will be descriptive and will be presented by study group.

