7.1.1. Analysis of demographics

Demographic characteristics (age at the first dose in years, gender and race), cohort description and other characteristics such as smoking/exposure history status, pulmonary function test baseline results, height, weight and previous vaccination with a pneumococcal vaccine or an influenza vaccine will be summarized by group using descriptive statistics:

- Frequency tables will be generated for categorical variables such as race;
- Mean, median and standard deviation will be provided for continuous data such as age.
- The distribution of subjects enrolled among the study sites will be tabulated as a whole and per group.
- Withdrawal status will be summarised by group using descriptive statistics:
 - The numbers of withdrawn subjects will be tabulated according to the reason for withdrawal.
- The number of subjects enrolled into the study as well as the number of subjects excluded from ATP analyses will be tabulated.

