7.1.3.1. Humoral immune response

Within group evaluation

For each group, at each time point during which blood samples are collected for humoral immune response and for each assay:

- Seropositivity rate and their exact 95% CI will be tabulated.
- GMCs and their 95% CI will be calculated.
- Antibody concentrations distribution will be investigated using Reverse Cumulative Curves.

These analyses will also be performed for each level of the following minimisation factors: age (50-59 years vs. 60-70 years), smoking status (current vs. former smoker), FEV₁/FCV ratio (≥ 0.7 vs. < 0.7).

Between groups evaluation (only for Step 2)

Comparative analyses will be exploratory with the aim to characterise the difference between the 10-10-10-AS and 10-10-3-AS groups in humoral immune response.

The difference in terms of GMCs will be evaluated, one month post-Dose 2, by computing the 95% CIs of the GMC ratio between groups for Step 2 by using a one-way ANCOVA model on the logarithm10 transformation of the concentrations/ titres. The ANCOVA model will include the group category, the age category, the smoking status and FEV₁/FVC (≥ 0.7 or < 0.7) and the pre-Dose 1 concentration (as covariate) as fixed effects. The groups will be considered significantly different if the 95% CI for the GMC ratio between the two groups does not contain the value 1.

However, these differences should be interpreted with caution considering that there will be no adjustment for multiplicity of endpoints.

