7.2. Analysis up to Visit 8 (Day 420)

The final analyses will be descriptive and will be presented by study group, with pooled data from the two steps for the placebo groups.

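### The SAP pools placebo over two separately randomised steps in non-overlapping populations, so the displayed placebo column matches neither step's vaccine groups

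*SAP*

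**What the plan says.** Protocol 10.6 sets the presentation rule without any pooling: "The final analyses will be descriptive and will be presented by study group". SAP Amendment 2 extends it. Section 7.1 (Day 90) reads "The final analyses will be descriptive and will be presented by study group, with pooled data from the two steps for the placebo groups", and section 7.2 (Day 420) again has results presented "with pooled data from the two steps for the placebo groups". The group table in SAP section 3 lists PLACE1 and PLACE2 as separate entries, each with its own order and label. Under the heading "Pooled Groups label in tables" it gives both the single label Placebo. No reason, weighting or stratification is offered, and SAP section 10 declares no change from the planned analyses.

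The design keeps the steps apart. Protocol 5.2.2.1 provides one randomisation list per step, and 5.2.2.2.1 refers to "eligible subjects who will be randomly assigned per step": 1:1 in Step 1 (10-10-10 and PLACE1, about 15 each) and 1:1:1 in Step 2 (10-10-10-AS, 10-10-3-AS and PLACE2, about 30 each). Protocol 1.2.3 gives the role of placebo: it is included "as a control for both safety and immunogenicity assessments".

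**The concern.** Each vaccine group has its own randomised, concurrent placebo group. Pooling adds placebo subjects from the other step, who were never randomised against that vaccine group and were enrolled under different criteria. Step 1 takes healthy adults of 18-40. Step 2 takes adults of 50-70 with at least 10 pack-years, and opens only after a favourable safety evaluation of all Step 1 subjects. Step 2 allocation is minimised on age, smoking status, centre and FEV1/FVC so that PLACE2 resembles the adjuvanted groups. Adding about 15 younger subjects from outside that scheme undoes the balance in the displayed column.

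Safety description is the primary objective, and no adjusted vaccine-placebo model is planned that would repair the reference. The laboratory tables illustrate the risk. Protocol 4.3.2 warns that pre-existing laboratory abnormalities may be found in Step 2 subjects. If out-of-range values are more common there, pooling raises the placebo figure beside 10-10-10, the first human exposure to UspA2, and lowers it beside the adjuvanted groups. The two errors run in opposite directions, and the pooled column alone does not allow either to be undone.

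**Working it through.** **Inputs.** Planned placebo sizes are 15 (PLACE1) and 30 (PLACE2), from Protocol 5.2.2.2.1. Age ranges are 18-40 and 50-70, from Protocol 4.2.1 and 4.2.2. Intervals are two-sided 95%, exact for proportions. The documents give no placebo event rates or GMCs by step, so those below are assumptions shown as a range.

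**The plan's own figures.** Protocol 10.3 gives about 78.5% for detecting an AE of 5% incidence with 30 subjects: 1 − 0.95^30 = 0.785, reproduced. All 16 rows of Table 23 (exact intervals for n = 15) also reproduce. These calculations use groups of 15 and 30; none relies on a pooled placebo of 45.

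**Composition.** 15/45 = 33.3% from Step 1 and 30/45 = 66.7% from Step 2. Two thirds of the reference beside 10-10-10, and one third of that beside each adjuvanted group, therefore comes from the other step.

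**Age (fixed by design).** The pooled mean is m1/3 + 2·m2/3, which lies (2/3)(m2 − m1) above PLACE1 and (1/3)(m2 − m1) below PLACE2. The smallest gap the ranges allow is about 50 − 40 = 10 years, giving at least about 6.7 and 3.3 years. At the range midpoints (29 and 60) the pooled mean is (15·29 + 30·60)/45 = 49.7 years, which is 20.7 above PLACE1 and 10.3 below PLACE2. It falls between the two eligibility ranges.

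**Event rates (assumed).** Pooled rate = (15·p1 + 30·p2)/45. With d = p2 − p1, the shift is +(2/3)d against PLACE1 and −(1/3)d against PLACE2. For example, p1 = 10% and p2 = 30% pool to 23.3%.

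| Assumed d (points) | Shift against PLACE1 | Shift against PLACE2 |
|---|---|---|
| 0 | 0 | 0 |
| 10 | +6.7 | −3.3 |
| 20 | +13.3 | −6.7 |

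A negative d reverses the signs.

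**GMCs (assumed).** Pooled GMC = G1^(1/3) × G2^(2/3). With r = G2/G1, pooled/G1 = r^(2/3) and pooled/G2 = r^(−1/3).

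| Assumed r | Pooled / PLACE1 | Pooled / PLACE2 |
|---|---|---|
| 1 | 1.00 | 1.00 |
| 1.5 | 1.31 | 0.87 |
| 3 | 2.08 | 0.69 |

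**Which outputs are touched.**
- The ANCOVA of SAP 7.1.3.1 characterises the difference between the two adjuvanted groups. The summary score uses those two groups only. Holding rules are checked within investigational groups during the safety reviews, and CMI is sampled in Step 2 only. None of these uses pooled placebo.
- The serology tables by age, smoking status and FEV1/FVC hold Step 2 subjects only, so their placebo is PLACE2.
- What remains is the overall safety, laboratory, demographic and serology tables. The demographic tables include "other characteristics such as smoking/exposure history status, pulmonary function test baseline results, height, weight". Smoking and spirometry are recorded in Step 2 only, so about 15 of the 45 pooled subjects have neither.

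**Precision given up by splitting.** With zero events the exact upper limit is 1 − 0.025^(1/n).

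| Placebo column | Zero events: upper limit | 20% observed: 95% interval |
|---|---|---|
| PLACE1, n = 15 | 21.8% | 4.3-48.1% (3/15) |
| PLACE2, n = 30 | 11.6% | 7.7-38.6% (6/30) |
| Pooled, n = 45 | 7.9% | 9.6-34.6% (9/45) |

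**The case against.** The best counter-argument is that pooling may be additive. SAP section 3 gives PLACE1 and PLACE2 their own table order, label and step-specific footnote, which would be idle if the pooled column replaced them. Presentation by study group can be read as covering all five groups, with the pooled data alongside. On that reading Protocol 10.6 is met and there is nothing to declare. Table layout sits in the TFL annex, which is not among the published documents. This reading is possible and cannot be excluded. However, the governing sentence in 7.1 and 7.2 attaches pooling to the placebo groups and nowhere says that by-step columns are also shown. A programmer following it literally would produce the mixture.

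Other points stand in part:
- The rate and GMC shifts rest wholly on assumed differences, and zero is possible. The statement in Protocol 1.2.1 that age matters concerns response to a vaccine, not to saline.
- Both steps exclude laboratory abnormalities judged clinically significant, which narrows any difference. But SAP 7.1.2 counts every value outside the normal range, significant or not, so the abnormalities anticipated for Step 2 would still enter the tables.
- Missing smoking and spirometry data in Step 1 are not caused by pooling; 10-10-10 has none either.
- The analyses are descriptive and to be read with caution, and the decision to open Step 2 rests on unblinded Step 1 data before anyone in PLACE2 is vaccinated. That limits the harm to how the tables are read.
- Pooling does narrow the placebo interval. A labelled supplement keeps that benefit.

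**Conclusion.** The concern holds. As written, SAP 7.1 and 7.2 place a one-third/two-thirds mixture of two populations beside every vaccine group, including in the primary safety tables, without a reason and without declaring the departure from Protocol 10.6. The composition and the age displacement (at least about 6.7 years against PLACE1 and 3.3 against PLACE2) follow from the design at the planned sizes. Any distortion of rates or GMCs depends on unknown background differences and is nil if the two placebo groups behave alike. No formal comparison, holding rule or selection score is affected. The remaining uncertainty is whether the TFL already provides by-step columns. If it does, the defect reduces to wording that fails to say so. The change should be made, because it restores the randomised reference at little cost.

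**What to change.** In SAP 7.1 and 7.2, replace the pooling clause with:

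> Placebo will be presented by step: PLACE1 with 10-10-10; PLACE2 with 10-10-10-AS and 10-10-3-AS.

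Keep any pooled placebo column only as a supplement labelled as spanning both steps, and declare it in SAP section 10. If the TFL already shows PLACE1 and PLACE2 separately, state that in 7.1 and 7.2. The cost is one extra table column and the wider by-step placebo intervals set out in the check; the supplement leaves the narrower pooled interval available.
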